# 7.6 Analyses of Efficacy Endpoints

Efficacy analyses will be performed on the all-treated population. Sensitivity analyses may be performed based on the efficacy-evaluable population.

#### 7.6.1 Overall Response Rate

Best overall response is defined as the best disease outcome over all response assessments on or before the initiation of subsequent anticancer therapy. Best overall response categories include CR, PR, SD, and PD. The number and percentage of subjects in each best overall assessment category will be presented by treatment arm. ORR will be defined as the proportion of subjects who achieve a CR or PR according to the Lugano Classification for NHL (Cheson et al. 2014), as assessed by investigators. ORR will be calculated, and the corresponding 2-sided 95% confidence interval will be derived.

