4.2 INVESTIGATOR'S ASSESSMENT OF RESPONSE TO TREATMENT

The investigator must rate the response of the subject's response to treatment consistent with clinical guidelines (Cheson et al. 2014) as listed below in Table 6.

Overall response assessments will include evaluation of physical examinations, bone marrow assessments, and radiographic evaluations per the schedule of assessments. Subjects who have signs and symptoms of progression outside of the scheduled assessment should be evaluated by the investigator with a physical examination and response assessments (see Table 6) to determine if disease progression is present. Any suspected case of disease progression should be confirmed with a CT and/or PET/CT scan if one was not obtained and should be reported to the Sponsor or designee via the electronic data capture (EDC) system. Subjects may continue study treatment until progression is confirmed.

Table 6 Response Assessment Criteria for NHL (Cheson et al. 2014)

Response and Site	PET-CT-Based Response	CT-Based Response
Complete	Complete metabolic response	Complete radiologic response (all of the following)
Lymph nodes and extra lymphatic sites	Score 1, 2, or 3 ^a with or without a residual mass on 5PS ^b It is recognized that in Waldeyer's ring or extranodal sites with high physiologic uptake or with activation within spleen or marrow (e.g., with chemotherapy or myeloid colony-stimulating factors), uptake may be greater than normal mediastinum and/or liver. In this circumstance, complete metabolic response may be inferred if uptake at sites of initial involvement is no greater than surrounding normal tissue even if the tissue has high physiologic uptake.	Target nodes/nodal masses must regress to ≤1.5 cm in LDi No extralymphatic sites of disease
Nonmeasured lesion	Not applicable	Absent
Organ enlargement	Not applicable	Regress to normal
New lesions	None	None
Bone marrow	No evidence of FDG-avid disease in the marrow	Normal by morphology; if indeterminate, IHC negative
Partial	Partial metabolic response	Partial remission (all of the following)
Lymph nodes and extra lymphatic sites	Score 4 or 5 ^b with reduced uptake compared with baseline and residual mass(es) of any size At interim, these findings suggest	≥50% decrease in SPD of up to 6 target measurable nodes and extranodal sites

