  - If there are <2 of 6 subjects with DLTs, then approximately 14 additional subjects will be enrolled and treated with lenalidomide 10 mg QD for Cycles 1 through 12.
- If there are <2 of 6 subjects with DLTs on 15 mg QD, 6 additional subjects are planned to be enrolled to receive an increased dose of lenalidomide at 20 mg QD.
  - o If there are ≥2 subjects with DLTs, the dose of lenalidomide will be reduced back to 15 mg QD. Approximately 14 more subjects will be added to complete enrollment at the 15-mg QD dose.
  - If there are <2 of 6 subjects with DLTs, 20 mg of lenalidomide will be the dose used for Cycles 2 through 12. Approximately 14 more subjects will be added to complete enrollment.

Note: Subjects will be evaluated for DLTs at the end of the first cycle, on a rolling basis, when they complete a cycle of treatment.

For both parts, twenty-eight days is one cycle. Treatment with acalabrutinib may be continued until confirmed disease progression or an unacceptable drug-related toxicity occurs. Please refer to CSP Appendices 5 and 6 for the complete schedule of assessments.

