#### 7.6.2 Duration of Response

The DOR is defined as the interval from the first documentation of CR or PR to the earlier of the first documentation of definitive disease progression or death from any cause. Following first documentation of CR or PR, subjects who do not experience a disease progression or death will be censored using the same rule for PFS as described in Table 1. DOR is calculated as date of disease progression or death (censoring date for censored subjects) – date of achieving the first CR, CRi, PR, or nPR + 1. Kaplan-Meier (KM) methods similar to those described in Section 7.6.3 will be used to estimate event-free curves and corresponding quantiles (including the median) by

arm.

If at least 1 responder has an event of death (and without progression prior to death) due to Coronavirus disease 2019 (COVID-19), a sensitivity analysis will be conducted to assess for the potential impact of deaths due to COVID-19. Subjects with death related to COVID-19 infection (and without progression prior to death) will be censored at their last evaluable assessment prior to their COVID-19 related death date.

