# 7.6.3 Progression-Free Survival

PFS is defined as the interval from the first dose date of any study drug to the earlier of the first documentation of objective disease progression or death from any cause.

Subjects who do not have disease progression or death at or prior to data analysis cutoff date will be censored according to Table 1.

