**Table 1. PFS Censoring** 

Situation Date of Event or Censoring Outcome			
Situation 1: PFS events include death or first disease progression as assessed by			
investigator that occurred at or prior to the earliest of data analysis cutoff date,			
alternative cancer therapy start date, and discontinuation from study (and not			
immediately following ≥2 consecutively missed visits where CT scan was required).			
Date of event is defined as follows:			
Death before first disease assessment	Date of death	Event	
INV-PD or death before study exit or	Earlier date of INV-PD or death	Event	
data cutoff			
Situation 2: All other cases not meeting	ng 'Situation 1' will be censored as	follows:	
No baseline assessment	First dose date of any study	Censored	
No baseline assessment	drug	Censored	
No adequate* post-baseline	First dose date of any study	Censored	
assessment		Censored	
	drug		
No INV-PD or death at the time of data	Date of last adequate* INV	Censored	
cutoff	assessment before data cutoff		
No INV-PD or death before lost to	Date of last adequate* INV	Censored	
follow-up or study exit	assessment before lost to		
	follow-up or study exit		

No INV-PD or death before start of	Date of last adequate* INV	Censored
subsequent anticancer therapy	assessment before start of	
	subsequent anticancer therapy	
INV-PD or death immediately after two	Date of last adequate* INV	Censored
INV-PD or death immediately after two or more consecutively missed visits	Date of last adequate* INV assessment before missing two	Censored

Abbreviation: INV=investigator

PFS will be calculated as date of disease progression or death (censoring date for censored subjects) – date of first dose of any study drug + 1.

Kaplan-Meier methods will be used to estimate the event-free curves by arm and corresponding quantiles (including the median). The proportion of subjects who are progression-free and the corresponding 95% CI will be estimated based on KM method at select timepoints by treatment arm.

If at least 1 subject has an event of death (and without progression prior to death) due to COVID-19, a sensitivity analysis will be conducted to assess for the potential impact of deaths due to COVID-19. Subjects with death related to COVID-19 infection (and without progression prior to death) will be censored at their last evaluable assessment prior to their COVID-19 related death date.

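### Best overall response for ORR (Part 2 primary endpoint) does not stop at investigator-assessed progression, so a CR or PR recorded after PD counts as a response although PFS has an event at that PD

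*SAP*

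**What the plan says.** SAP 7.6.1 takes best overall response as "the best disease outcome over all response assessments on or before the initiation of subsequent anticancer therapy". The categories are CR, PR, SD and PD. ORR is the proportion with CR or PR by Lugano criteria, as judged by the investigator. PD is a possible outcome but does not close the window. Protocol 5.5.4 defines ORR without a cut at PD, and SAP section 8 (changes from the protocol) is silent on the point.

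PFS works differently. SAP 7.6.3 ends it at "the first documentation of objective disease progression or death from any cause", and Table 1 says that "PFS events include death or first disease progression as assessed by" the investigator. Table 1 does not count a PD that comes after new therapy, study exit or data cutoff. It also censors "INV-PD or death immediately after two or more consecutively missed visits". Nothing in the SAP says that a later CR or PR cancels an earlier PD, or what happens when a PD call is later judged not confirmed.

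On continuing after a suspected progression, Protocol 4.2 states: "Subjects may continue study treatment until progression is confirmed". SAP 3.1 is similar: "Treatment with acalabrutinib may be continued until confirmed disease progression or an unacceptable drug-related toxicity occurs".

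**The concern.** Two endpoints built from the same investigator assessments can contradict each other for one subject. Take PD at one assessment and PR at a later one, with no new therapy between them. PFS has an event at the PD. ORR counts a responder, and because SAP 7.6.2 starts DOR at the first CR or PR, that subject's DOR begins after the PFS event.

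In Part 2 this touches the primary endpoint, and the cohort has no control arm, so the response rule alone determines the reported activity. The effect goes one way: extra assessments after PD can turn a non-responder into a responder but never the reverse. Without a stated rule on unconfirmed PD, the programmer would have to settle such a case after seeing the data.

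**Working it through.** The documents state no figure for this point, so there is none to reproduce. The check has three steps.

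**1. Direction.** Let A be a subject's assessments up to and including the first investigator-assessed PD, and B all assessments up to new anticancer therapy. When PD comes before new therapy, A is contained in B, so the best outcome over B is at least as good as over A. Hence ORR under the written rule is at least as high as ORR with the window cut at PD.

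**2. Can it happen?** Setting the relevant sections side by side:

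- Protocol 4.1.22: progression suspected from examination or laboratory results must be confirmed by CT and/or PET/CT. Progression seen on PET/CT alone needs a second imaging modality or a biopsy. CT-suspected progression that cannot be biopsy-proven may go to PET/CT at the investigator's discretion.
- Protocol 4.2: treatment may continue while confirmation is pending.
- Protocol 4.4 and Appendix 5: after progression, follow-up covers next treatment and survival. The tumor assessment row is marked for disease follow-up, which is for subjects who stopped without progression, but not for long-term follow-up.

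The routes left are a PD call awaiting confirmation (chiefly PET/CT alone, or CT not biopsy-proven) and treatment or scans continued past PD. Neither is excluded, and neither should be common.

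**3. Size per subject.** Inputs: N up to 40 in Cohort 1 (SAP 3.2), and exact two-sided 95% intervals (SAP section 6). The base count is an assumption. Protocol 1.1 cites an ORR of 46% for ibrutinib in relapsed or refractory MZL; 0.46 × 40 = 18.4, taken as 18 responders with the window cut at PD. The number of post-PD responders is also assumed, from 0 to 2.

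| Post-PD responders | ORR as written | Exact 95% CI |
|---|---|---|
| 0 | 18/40 = 45.0% | 29.3 to 61.5 |
| 1 | 19/40 = 47.5% | 31.5 to 63.9 |
| 2 | 20/40 = 50.0% | 33.8 to 66.2 |

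The step is 1/40 = 2.5 points whatever the base. For example, 14/40 is 35.0% (20.6 to 51.7) and 22/40 is 55.0% (38.5 to 70.7), and one subject moves either by 2.5 points. The interval half-width at 18/40 is (61.5 − 29.3)/2 = 16.1 points.

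The same rule serves Part 3, where ORR is secondary. The step there is 1/32 = 3.1 points at N = 32 and 1/26 = 3.8 points at N = 26.

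**The case against.** The best counter-argument is that suspected progression is not recorded progression. In Protocol 4.2 the permission to continue treatment follows directly on the requirement to confirm a suspicion by scan, so it mainly covers the gap between clinical suspicion and imaging. If sites enter PD only once it is confirmed, little is left of the problem. This largely stands and is why the case should be rare. It does not remove the point, because the SAP nowhere limits recorded investigator PD to confirmed PD, and Table 1 uses the first one.

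A second argument is that the effect is small and nothing is tested. That is correct: 2.5 points per subject is well inside a half-width of about 16 points, and SAP 3.2 says the sample size is not power-based.

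A third is that closing the window at PD could err the other way. Protocol 3.5.6 warns of transient worsening when dosing is withheld, and Protocol 3.7.3 says lenalidomide tumor flare can resemble progression. This also stands. The fix therefore has to say how a revised PD call is treated.

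Some stronger readings are tempting but not supported:

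- A reader might infer that the plan allows treatment through radiographic progression, with responses routinely collected afterwards. The treatment rule and the follow-up schedule say otherwise.
- A reader might see three different progression events, because DOR refers to the "first documentation of definitive disease progression or death from any cause" while PFS and Table 1 use other words. SAP 4.1 applies one set of criteria to all efficacy endpoints, and no subject can be shown to be classified differently because of the adjective.
- A reader might expect DOR to come out negative when PD precedes the response. SAP 7.6.2 treats progression as something that follows the first CR or PR, so that reading is forced.
- A reader might add that SAP 6.1.4 counts only therapy begun after the last dose as subsequent. That definition is written for summary tables, and other anticancer therapy for NHL is prohibited on study (Protocol 3.6.2), so no practical consequence is shown.

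**Conclusion.** The point holds as a minor one. The written rule for the Part 2 primary endpoint credits a CR or PR recorded after an investigator-assessed PD, while PFS counts an event at that PD unless another Table 1 censoring condition applies. No other section of either document corrects this.

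The effect on ORR is zero or upward, at 2.5 points per affected subject at N = 40. The number affected is not known from the documents and may be zero; the 0 to 2 shown is an assumption, as is the base of 18/40. No error rate or decision rule is involved. The documents do not support a claim that ORR will be materially inflated, only that the rule is open to it and inconsistent with PFS when the case arises.

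**What to change.** In SAP 7.6.1, restrict best overall response to assessments up to and including the first investigator-assessed PD, or before the start of new anticancer therapy or the data cutoff if either is earlier. Use the same PD record as Table 1, and let it close the window even where Table 1 censors that PD after missed visits.

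Add that a PD call which the investigator later judges not confirmed and revises is not counted as PD in ORR, DOR or PFS. List any CR or PR recorded after first PD separately.

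The cost is a few sentences, a small programming change and one listing. The SAP is dated 31 March 2022 and Protocol 3.2 projects the final cut-off for about 25 August 2023, so the timetable left room to set the rule before final lock. The downside is that ORR may be slightly lower, and a transient worsening or tumor flare recorded as PD and never revised would count as non-response if no CR or PR came before it. The listing would show any such subject who later had a recorded CR or PR.

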#### 7.6.2 Duration of Response

The DOR is defined as the interval from the first documentation of CR or PR to the earlier of the first documentation of definitive disease progression or death from any cause. Following first documentation of CR or PR, subjects who do not experience a disease progression or death will be censored using the same rule for PFS as described in Table 1. DOR is calculated as date of disease progression or death (censoring date for censored subjects) – date of achieving the first CR, CRi, PR, or nPR + 1. Kaplan-Meier (KM) methods similar to those described in Section 7.6.3 will be used to estimate event-free curves and corresponding quantiles (including the median) by

arm.

If at least 1 responder has an event of death (and without progression prior to death) due to Coronavirus disease 2019 (COVID-19), a sensitivity analysis will be conducted to assess for the potential impact of deaths due to COVID-19. Subjects with death related to COVID-19 infection (and without progression prior to death) will be censored at their last evaluable assessment prior to their COVID-19 related death date.

# 7.6.3 Progression-Free Survival

PFS is defined as the interval from the first dose date of any study drug to the earlier of the first documentation of objective disease progression or death from any cause.

Subjects who do not have disease progression or death at or prior to data analysis cutoff date will be censored according to Table 1.

**Table 1. PFS Censoring** 

Situation Date of Event or Censoring Outcome			
Situation 1: PFS events include death or first disease progression as assessed by			
investigator that occurred at or prior to the earliest of data analysis cutoff date,			
alternative cancer therapy start date, and discontinuation from study (and not			
immediately following ≥2 consecutively missed visits where CT scan was required).			
Date of event is defined as follows:			
Death before first disease assessment	Date of death	Event	
INV-PD or death before study exit or	Earlier date of INV-PD or death	Event	
data cutoff			
Situation 2: All other cases not meeting	ng 'Situation 1' will be censored as	follows:	
No baseline assessment	First dose date of any study	Censored	
No baseline assessment	drug	Censored	
No adequate* post-baseline	First dose date of any study	Censored	
assessment		Censored	
	drug		
No INV-PD or death at the time of data	Date of last adequate* INV	Censored	
cutoff	assessment before data cutoff		
No INV-PD or death before lost to	Date of last adequate* INV	Censored	
follow-up or study exit	assessment before lost to		
	follow-up or study exit		

No INV-PD or death before start of	Date of last adequate* INV	Censored
subsequent anticancer therapy	assessment before start of	
	subsequent anticancer therapy	
INV-PD or death immediately after two	Date of last adequate* INV	Censored
INV-PD or death immediately after two or more consecutively missed visits	Date of last adequate* INV assessment before missing two	Censored

Abbreviation: INV=investigator

PFS will be calculated as date of disease progression or death (censoring date for censored subjects) – date of first dose of any study drug + 1.

Kaplan-Meier methods will be used to estimate the event-free curves by arm and corresponding quantiles (including the median). The proportion of subjects who are progression-free and the corresponding 95% CI will be estimated based on KM method at select timepoints by treatment arm.

If at least 1 subject has an event of death (and without progression prior to death) due to COVID-19, a sensitivity analysis will be conducted to assess for the potential impact of deaths due to COVID-19. Subjects with death related to COVID-19 infection (and without progression prior to death) will be censored at their last evaluable assessment prior to their COVID-19 related death date.

#### 7.6.4 Overall Survival

The duration of OS will be measured from the first dose date of any study drug until the date of death due to any cause. Subjects who were not known to have died prior to the analysis data cutoff date will be censored as detailed in Table 2.

Table 2. Overall Survival Censoring

Situation	Date of Event or Censoring	Outcome
Death before first disease assessment	Date of death	Event
Death between scheduled assessments	Date of death	Event

\*Assessment is adequate if it is not "Unknown/NA" or missing

All other cases will be censored as follows:			
Lost to follow-up immediately after	Randomization date	Censored	
randomization			
Not known to have died at or prior	Date last known alive before analysis	Censored	
to analysis data cutoff date	data cutoff date		
Known to have died, but death	Date last known alive before death	Censored	
date is missing month and day or			
is completely unknown			
Not known to have died prior to	Date last known alive before lost to	Censored	
lost to follow-up or study exit	follow-up or study exit		

OS will be calculated as death date (or censoring date) – first dose date of any study drug + 1.

OS will be analyzed in the same fashion as that for primary efficacy endpoint as described for PFS in Section 7.6.3.

If at least 1 subject has an event of death due to COVID-19, a sensitivity analysis will be conducted to assess for the potential impact of deaths due to COVID-19. Subjects with death related to COVID-19 infection will be censored at their date of death due to COVID-19.

#### 7.6.5 Time-to-Next Treatment

# 7.7 Analyses of Safety Endpoints

Safety analyses will be performed by treatment arm on the all-treated population.

Analyses of AEs will be performed on treatment-emergent AE (TEAE) data, unless otherwise specified. TEAEs are defined as those adverse events with onset or worsen date during the treatment emergent period, which is defined in Section 6.1.6. All AE terms will be coded by

MedDRA, and severity will be graded per CTCAE version 5.0.

#### 7.7.1 Adverse Events

Subject incidence of the following events will be tabulated by SOC and/or PT in descending order of frequency. Summaries will also be presented by the severity of the AE and by causality of study drug(s).

- TEAEs
- SAEs
- TEAEs related to study drug(s)
- SAEs related to study drug(s)
- TEAEs leading to study drug(s) discontinuation, dose modification, and delay
- Confirmed or suspected COVID-19 TEAEs
- Confirmed or suspected COVID-19 AEs (including those that are not treatment-emergent)
- COVID-19 associated TEAEs
- COVID-19 TEAEs leading to death

COVID-19 associated AEs are defined as all confirmed and suspected COVID-19 AEs, plus all other AEs occurring within <7 days before and <30 days after the start date of all the confirmed COVID-19 AEs

Summary tables and a listing will be provided when death is reported.

# 7.7.2 Adverse Events of Special Interest (AESIs) and Events of Clinical Interest (ECIs)

AESIs and ECIs are defined in Appendix 1. Subject incidence will be presented by treatment arm in the summary tables.

# 7.7.3 Laboratory Test Results

This study will primarily use central laboratory testing for laboratory evaluations. Samples from local laboratories will be used if central testing is unavailable. Analyses will be performed for laboratory test data collected at baseline and from first exposure to any study drug to 30 days after last dose (latest of any study drug) or up to the safety follow-up visit date, whichever is later. For hematology, serum chemistry, and T/8/NK cell count performed in the central laboratory, reference range and the results will be reported in standard international units. Generic normal ranges

(JAMA 2016) will be applied whenever reference ranges are not available (e.g., local laboratory data). Applicable laboratory test abnormalites will be graded according to CTCAE version 5.0.

For selected laboratory test parameters, summary statistics (mean, standard deviation, median, minimum and maximum) will be produced at baseline, post-baseline values from the last visit, minimum and maximum post-baseline values, and changes of these post-baseline values from baseline. Post-baseline toxicity grade greater than baseline grade will be presented in the treatment-emergent laboratory abnormality table. Shift from baseline to the maximum grade from first exposure to any study drug to 30 days after last dose (latest of any study drug) or up to the safety follow-up visit date, whichever is later, will be provided as shift tables for selected parameters.

In order to be included in the summary table, a subject must have at least one post-baseline value for the given time point.

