6.3.1 Adverse Event Reporting Period

AEs and SAEs will be collected by the site from time of signature of ICF throughout the treatment period and including the follow-up period. After the signing of the ICF and prior to the first dose of study drug, all SAEs, regardless of causality, must be reported to the Sponsor.

All AEs and SAEs will be reported from first dose of study treatment until 30 days after the last dose of study drug(s) or the start of new anticancer therapy (whichever comes first). After this period, investigators should report SAEs that are believed to be related to the study drug(s) or any AEs of concern (deemed by the Sponsor or investigator), regardless of causality to the study drug(s) as relevant.

All SAEs that occur during the reporting period should be followed to resolution or until the investigator assesses the subject as stable or the subject is lost to follow-up or withdraws consent. Resolution/stable means the subject has returned to baseline state of health or the investigator does not expect any further improvement or worsening of the event.

All SAEs/AESIs will be recorded and reported to the sponsor or designee within 24 hours. The investigator will submit any updated SAE/AESI data to the sponsor within 24 hours of it being available.

Investigators are not obligated to actively seek AE or SAE data in former study subjects. However, if at any time after a subject's last visit the investigator learns of any SAE, including a death, that is considered to be reasonably related to the study treatment or study participation, the investigator may notify the Sponsor.

After the final DCO, the study will transition to the PTAP. Patients will be managed as per standard of care. All SAEs, irrespective of attribution of causality, will be collected and recorded in the subject's medical records. SAEs will be reported to the sponsor using a paper form via Fax or email. No AEs will be reported during the PTAP phase of the study.

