#### 6.1.3 Definition of Prior and Concomitant Medication

For the purpose of inclusion in prior and/or concomitant medication summaries, incomplete medication start and stop dates will be imputed as detailed in Section 6.2. Based on imputed start and stop dates:

- Prior medications are defined as medications with a start date occurring before the date of first dose of any study drug.
- Concomitant medications are defined as medications that:
  - Had start date on or after the first dose date of study drug and either within 30 days after the last dose date (latest of any study drug), or before the first dose date of subsequent anticancer therapy, whichever is earlier, or
  - Had start date before first dose date of any study drug and were either ongoing or had a stop date on or after first dose date.
- Medications that meet the criteria for both prior and concomitant medication will be classified as both prior and concomitant medication.
- Medications with completely missing start and stop dates will be considered as both prior and concomitant medications.

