# **6.1.5 Treatment Emergent Period**

The treatment emergent period is defined as the period of time from the date of the first dose of any study drug through either 30 days after the date of the last dose (latest of any study drug) or the first date of subsequent anticancer therapy, whichever is earlier.

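### Laboratory, vital-sign and ECOG summaries (SAP 7.7.3 to 7.7.5) do not stop at subsequent anticancer therapy, so values from the next regimen can be counted as study-treatment values without a flag

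*SAP*

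**What the plan says.** SAP 7.7.3 (laboratory), 7.7.4 (vital signs) and 7.7.5 (ECOG) share one window. It opens at first exposure to any study drug and closes at "30 days after last dose (latest of any study drug) or up to the safety follow-up visit date, whichever is later". Within it the SAP takes:

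- for laboratory tests and vital signs, "post-baseline values from the last visit, minimum and maximum post-baseline values" and their changes from baseline;
- for laboratory grades, a shift table: "Shift from baseline to the maximum grade from first exposure to any study drug to 30 days after last dose", or to the safety visit if that is later;
- for ECOG, a shift to the maximum score;
- for laboratory grades again, "Post-baseline toxicity grade greater than baseline grade will be presented in the treatment-emergent laboratory abnormality table".

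Related windows close at new therapy:

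- SAP 6.1.5 ends the treatment-emergent period 30 days after last dose "or the first date of subsequent anticancer therapy, whichever is earlier".
- SAP 6.1.3 limits concomitant medications started on study to those within 30 days of last dose "or before the first dose date of subsequent anticancer therapy, whichever is earlier".
- The narrative window in SAP Appendix 2 also closes at new therapy, with exceptions for related SAEs and clinically significant AEs.
- Protocol 6.3.1 has all AEs and SAEs reported "until 30 days after the last dose of study drug(s) or the start of new anticancer therapy (whichever comes first").

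SAP 7.7 applies the treatment-emergent period to adverse events only: "TEAEs are defined as those adverse events with onset or worsen date during the treatment emergent period".

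Protocol 4.3 and footnote d of Appendices 5 and 6 require the safety follow-up visit 30 (+7) days after last dose whether or not new treatment has begun. Both appendices schedule vital signs, ECOG, hematology and serum chemistry at that visit.

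**The concern.** The protocol deliberately collects data after a switch of therapy, and that is sound. The problem lies in the summaries. A blood count taken under the next regimen can supply a subject's worst grade, minimum, maximum or last value, and nothing in the table or the planned listings marks it. A reader would take it for an effect of study drug.

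The two safety windows can also treat one observation differently. A cytopenia that first appears after the switch is outside the treatment-emergent period as an adverse event, yet inside the window as a laboratory grade. The laboratory table that carries the treatment-emergent label makes this most awkward, because it uses the SAP 6.1.5 term inside a section with a longer window.

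Safety is the primary objective of Part 3 and a secondary objective of Part 2, so these tables will be read even though they are supportive.

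**Working it through.** **Inputs**

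- Earliest subsequent therapy: last dose + 1 day, since SAP 6.1.4 requires a start after last dose.
- Safety follow-up visit: day 30 to 37 after last dose (Protocol 4.3).
- Denominators: up to 40 in Part 2 Cohort 1, about 26 to 32 in Part 3 (Protocol 5.2, SAP 3.2).

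The documents give no overrun figure, so there is none to reproduce.

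**Window ends, in days after last dose, with new therapy on day k**

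- Adverse events (SAP 6.1.5): min(30, k).
- Laboratory, vital signs, ECOG (SAP 7.7.3 to 7.7.5): max(30, visit day), which is 30 to 37.
- Time under the next regimen inside the second window, for k up to 30: from 30 − k to 37 − k days.

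| New therapy on day k | Visit on day 30 | Visit on day 37 |
|---|---|---|
| 1 | 29 days | 36 days |
| 14 | 16 days | 23 days |
| 28 | 2 days | 9 days |

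The maximum is 37 − 1 = 36 days for a visit held on schedule. The SAP does not cap the visit date, so a late visit would lengthen it.

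**One illustrative subject.** New therapy starts on day 14 and the safety visit is on day 30. A Grade 3 neutrophil count first appears at that visit.

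- As an adverse event: min(30, 14) = 14, and day 30 is later, so it is not a TEAE.
- As a laboratory grade: max(30, 30) = 30, so it is included and sets the subject's maximum grade.

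**Effect on a table row.** A worst-grade row changes only if new therapy starts before the visit, a sample follows it, and that sample exceeds the subject's earlier maximum. Each such subject moves the row by:

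- Part 2 Cohort 1: 1/40 = 2.5 percentage points.
- Part 3 total: 1/32 = 3.1 to 1/26 = 3.8 percentage points.

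**Imputed dates.** SAP 6.2.1 sets a year-only therapy date to 30 June, or to last dose + 1 if 30 June falls before last dose. Take a last dose on 1 July and a true start on 31 December. The imputed start is 2 July, which is 182 days too early. A stop applied to that date would close the window on day 1 instead of day 30 to 37 and discard 29 to 36 days of valid data. Any stop rule therefore has to deal with imputed dates.

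**The case against.** The strongest reply is that the window is intended. The same wording appears in all three sections, the SAP writes a new-therapy stop where it wants one, and the protocol orders the visit irrespective of new treatment. A longer window can catch late effects of study drug, and truncation can only lower worst grades or leave them unchanged, which is the less cautious direction for safety. Nor is there a uniform stop rule: Protocol 4.1.4 collects concomitant medications for 30 days after last dose with no such stop. The treatment-emergent laboratory table has its own criterion, so its label need not import SAP 6.1.5. Finally, 36 days is an extreme, and the schedule has a single safety follow-up visit after end of treatment, so a switcher would usually contribute one sample set.

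Much of this stands. The windows are misaligned rather than contradictory, the laboratory table is at worst ambiguous, and the practical effect may be small. A flag without truncation would meet part of the concern.

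It does not remove the problem. Consistent wording does not make the attribution right. By-subject listings and recorded therapy dates let a reviewer trace a value by hand, but they do not correct the tables. The case for catching late effects holds for subjects who have not switched; after a switch, a single value cannot separate a late study-drug effect from an effect of the new regimen.

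**Conclusion.** The concern holds, at minor severity. Under the stated rule, values drawn up to 36 days into the next regimen can enter the laboratory, vital-sign and ECOG summaries unflagged. That maximum assumes new therapy the day after last dose and a visit on the last scheduled day.

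The per-subject effects assume full planned enrolment. SAP section 6 also calls for summaries by treatment arm. If Part 3 dose levels are tabulated separately, one subject in a six-subject group moves a row by 1/6 = 16.7 points.

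The documents give no rate of switching before the safety visit, so no number of affected subjects is claimed. The TEAE, DLT and ORR analyses do not use this window and are unaffected.

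**What to change.** 1. In SAP 7.7.3 to 7.7.5, close the summary window at the first date of subsequent anticancer therapy, that date included as in SAP 6.1.5, whenever it comes before the current end. Keep the extension to the safety visit for everyone else.
2. State in SAP 7.7.3 that the treatment-emergent laboratory table uses this window. For subjects who do not switch it can still run up to 7 days past the adverse-event window (37 − 30), so the text should define it explicitly rather than rely on the label.
3. Present post-switch values in a flagged listing so that none is lost.
4. Do not drop a value solely because of an imputed therapy date. Keep it in the tables and flag it in the listing.

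The cost is one clause in three sections, one listing and one rule for imputed dates; no new data are needed. There are two drawbacks. For early switchers, a late study-drug effect seen at the safety visit moves from the tables to the listing. Subjects with imputed therapy dates are also handled differently from those with complete dates, which a table footnote should state.
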